7.2.4.2 Evaluation of Non-target Lesions

Definitions for assessment of response for non-target lesion(s) are as follows:

- Complete Response (CR): The disappearance of all non-target lesions. All lymph nodes identified as a site of disease at baseline must be non-pathological (i.e., a short axis of <10 mm).
- Non-CR/Non-PD: The persistence of 1 or more non-target lesion(s) or lymph nodes identified as a site of disease at baseline with a short axis of ≥ 10 mm.
- Progressive Disease (PD): Unequivocal progression of existing non-target lesions.

- Not Applicable (NA): No non-target lesions at baseline.
- Not Evaluable (NE): Cannot be classified by one of the 4 preceding definitions.

Note:

- In the presence of measurable disease, progression on the basis of solely non-target disease requires substantial worsening such that even in the presence of SD or PR in target disease, the overall tumor burden has increased sufficiently to merit discontinuation of therapy.
- Sites of non-target lesions, which are not assessed at a particular time point based on the assessment schedule, should be excluded from the response determination (i.e., non-target response does not have to be NE).

7.2.4.3 New Lesions

New malignancies denoting disease progression must be unequivocal. Lesions identified in follow-up in an anatomical location not scanned at baseline are considered new lesions. Any equivocal new lesions should continue to be followed. Treatment can continue at the discretion of the investigator until the next scheduled assessment. If at the next assessment the new lesion is considered to be unequivocal, progression should be documented.

7.2.4.4 Evaluation of Overall Response

Table 21 presents the overall response at an individual time point for all possible combinations of tumor responses in target and non-target lesions with or without the appearance of new lesions for subjects with measurable disease at baseline.

Table 21 Evaluation of Overall Response for Subjects with Measurable Disease at Baseline

Target Lesions	Non-target Lesions	New Lesions	Overall Response
CR	CR or NA	No	CR
CR	Non-CR/Non-PD or NE	No	PR
PR	Non-PD or NA or NE	No	PR
SD	Non-PD or NA or NE	No	SD
NE	Non-PD or NA or NE	No	NE
PD	Any	Yes or No	PD
Any	PD	Yes or No	PD
Any	Any	Yes	PD

Abbreviations: CR = complete response; NA = not applicable; NE = not evaluable; PD = progressive disease; PR = partial response; SD = stable disease.

Note:

- Subjects with a global deterioration of health status requiring treatment discontinuation without objective evidence of disease progression at that time should be classified as having “symptomatic deterioration.” Objective response status is determined by evaluations of disease burden. Every effort should be made to document the objective progression even after treatment discontinuation.
- In some circumstances, it may be difficult to distinguish residual disease from normal tissue. When the evaluation of CR depends on this determination, it is

recommended that the residual lesion be investigated (e.g., fine needle aspirate/biopsy) to confirm the CR.

7.2.4.5 Evaluation of Best Overall Response

The best overall response is the best response recorded from the start of the treatment until disease progression, death, or withdrawal of consent, whichever occurs first. Best overall response will be determined programmatically by Novartis based on the investigator's assessment of response at each time point.

- To be assigned a status of SD, follow-up disease assessment must have met the SD criteria at least once after enrollment for a minimum of 49 days.
- If the minimum time for SD is not met, best response will depend on the subsequent assessments. For example, if an assessment of PD follows the assessment of SD and SD does not meet the minimum time requirement, the best response will be PD. Alternatively, subjects lost to follow-up after an SD assessment not meeting the minimum time criteria will be considered NE.

Confirmation Criteria:

- To be assigned a status of PR or CR, a confirmatory disease assessment should be performed no less than 4 weeks (28 days) after the criteria for response are first met.

7.3 Safety

7.3.1 Safety Endpoints

The secondary objectives of the study include characterizing the safety of dabrafenib and trametinib combination therapy. As a consequence, clinical assessments including vital signs and physical examinations, 12-lead ECG, ECHO, chemistry and hematology laboratory values, and AEs will be monitored and evaluated. AEs will be graded by the investigator according to the NCI CTCAE, version 4.0.

7.3.2 Adverse Events

The investigator or site staff will be responsible for detecting, documenting and reporting events that meet the definition of an AE or SAE as outlined in Section 7.3.2.1 and Section 7.3.2.2 respectively.

7.3.2.1 Definition of an AE

Any untoward medical occurrence in a patient or clinical investigation subject, temporally associated with the use of a medicinal product, whether or not considered related to the medicinal product.

Note: An AE can therefore be any unfavorable and unintended sign (including an abnormal laboratory finding), symptom, or disease (new or exacerbated) temporally associated with the use of a medicinal product. For marketed medicinal products, this also includes failure to produce expected benefits (i.e., lack of efficacy), abuse or misuse.

Events meeting the definition of an AE include:

- Exacerbation of a chronic or intermittent pre-existing condition including either an increase in frequency and/or intensity of the condition
- New conditions detected or diagnosed after study treatment administration even though it may have been present prior to the start of the study
- Signs, symptoms, or the clinical sequelae of a suspected interaction
- Signs, symptoms, or the clinical sequelae of a suspected overdose of either study treatment or a concomitant medication (overdose per se will not be reported as an AE/SAE) unless this is an intentional overdose taken with possible suicidal/self-harming intent. This should be reported regardless of sequelae.

“Lack of efficacy” or “failure of expected pharmacological action” per se is not to be reported as an AE or SAE. However, the signs and symptoms and/or clinical sequelae resulting from lack of efficacy will be reported if they fulfil the definition of an AE or SAE.

Events that **do not** meet the definition of an AE include:

- Medical or surgical procedure (e.g., endoscopy, appendectomy); the condition that leads to the procedure is an AE
- Situations where an untoward medical occurrence did not occur (social and/or convenience admission to a hospital)
- Anticipated day-to-day fluctuations of pre-existing disease(s) or condition(s) present or detected at the start of the study that do not worsen
- The disease/disorder being studied, or expected progression, signs, or symptoms of the disease/disorder being studied, unless more severe than expected for the subject’s condition

7.3.2.2 Definition of an SAE

A serious adverse event is any untoward medical occurrence that, at any dose:

- a. Results in death

NOTE: Death due to disease under study is to be recorded on the Death CRF form and does not need to be reported as an SAE

- b. Is life-threatening

NOTE: The term 'life-threatening' in the definition of 'serious' refers to an event in which the subject was at risk of death at the time of the event. It does not refer to an event, which hypothetically might have caused death, if it were more severe.

- c. Requires hospitalization or prolongation of existing hospitalization

NOTE: In general, hospitalization signifies that the subject has been detained (usually involving at least an overnight stay) at the hospital or emergency ward for observation and/or treatment that would not have been appropriate in the physician’s office or

out-patient setting. Complications that occur during hospitalization are AEs. If a complication prolongs hospitalization or fulfills any other serious criteria, the event is serious. When in doubt as to whether “hospitalization” occurred or was necessary, the AE should be considered serious.

Hospitalization for elective treatment of a pre-existing condition that did not worsen from baseline is not considered an AE.

d. Results in disability/incapacity, or

NOTE: The term disability means a substantial disruption of a person’s ability to conduct normal life functions. This definition is not intended to include experiences of relatively minor medical significance such as uncomplicated headache, nausea, vomiting, diarrhea, influenza, and accidental trauma (e.g. sprained ankle) which may interfere or prevent everyday life functions but do not constitute a substantial disruption.

e. Is a congenital anomaly/birth defect

f. Medical or scientific judgment should be exercised in deciding whether reporting is appropriate in other situations, such as important medical events that may not be immediately life-threatening or result in death or hospitalization but may jeopardize the subject or may require medical or surgical intervention to prevent one of the other outcomes listed in the above definition. These should also be considered serious. Examples of such events are invasive or malignant cancers, intensive treatment in an emergency room or at home for allergic bronchospasm, blood dyscrasias or convulsions that do not result in hospitalization, or development of drug dependency or drug abuse.

g. Protocol-specific SAEs:

- All events of possible drug-induced liver injury with hyperbilirubinemia defined as ALT $\geq 3xULN$ **and** bilirubin $\geq 2xULN$ ($>35\%$ direct) (or ALT $\geq 3xULN$ and INR >1.5 , if INR measured) or termed ‘Hy’s Law’ events (INR measurement is not required and the threshold value stated will not apply to patients receiving anticoagulants).

Note: bilirubin fractionation is performed if testing is available. If testing is unavailable, record presence of detectable urinary bilirubin on dipstick indicating direct bilirubin elevations and suggesting liver injury. If testing is unavailable and a subject meets the criterion of total bilirubin $\geq 2xULN$, then the event is still reported as an SAE. If INR is obtained, include values on the SAE form. INR elevations >1.5 suggest severe liver injury.

- Any new primary cancers and treatment emergent malignancies (including squamous cell carcinoma and new primary melanoma) with the exception of basal cell carcinoma (BCC). BCC should be reported as an AE or SAE based on the discretion of the investigator.
- Symptomatic LVEF decrease that meets stopping criteria or asymptomatic LVEF decrease that does not recover, as outlined as LVEF guidance (Section 5.8.3.1)
- Retinal pigment epithelial detachment (RPED) or retinal vein occlusion (RVO)

7.3.3 Laboratory and Other Safety Assessment Abnormalities Reported as AEs and SAEs

Any abnormal laboratory test results (hematology, clinical chemistry, or urinalysis) or other safety assessments (e.g., ECGs, radiological scans, vital signs measurements), including those that worsen from baseline, and felt to be clinically significant in the medical and scientific judgement of the investigator are to be recorded as AEs or SAEs in accordance with the definitions provided.

In addition, an associated AE or SAE is to be recorded for any laboratory test result or other safety assessment that led to an intervention, including permanent discontinuation of study treatment, dose reduction, and/or dose interruption/delay.

Any new primary cancer must be reported as an SAE.

However, any clinically significant safety assessments that are associated with the underlying disease, unless judged by the investigator to be more severe than expected for the subject's condition, are **not** to be reported as AEs or SAEs.

7.3.4 Cardiovascular Events

Investigators will be required to fill out event specific data collection tools for the following AEs and SAEs:

- Myocardial infarction/unstable angina
- Congestive heart failure
- Arrhythmias
- Valvulopathy
- Pulmonary hypertension
- Cerebrovascular events/stroke and transient ischemic attack
- Peripheral arterial thromboembolism
- Deep venous thrombosis/pulmonary embolism
- Revascularization

This information should be recorded in the specific cardiovascular eCRF within one week of when the AE/SAE(s) are first reported.

7.3.5 Death Events

In addition, all deaths that occur whether or not they are considered SAEs will require a specific death data collection tool to be completed. The death data collection tool includes questions regarding cardiovascular (including sudden cardiac death) and noncardiovascular death.

This information should be recorded in the specific death eCRF within one week of when the death is first reported.

7.3.6 Disease-Related Events and/or Disease-Related Outcomes Not Qualifying as SAEs

An event which is part of the natural course of the disease under study (i.e., disease progression or hospitalization due to disease progression) does not need to be reported as an SAE.

Death due to disease under study is to be recorded on the Death eCRF form and does not need to be reported as an SAE.

If however, the underlying disease (i.e., progression) is greater than that which would normally be expected for the subject, or if the investigator considers that there was a causal relationship between treatment with study medication(s) or protocol design/procedures and disease progression, then this must be reported as an SAE.

7.3.7 Pregnancy Testing, Prevention and Reporting

7.3.7.1 Pregnancy Testing and Prevention

The need for a screening pregnancy test depends on whether a female subject is of childbearing potential or non-childbearing potential.

A female of non-childbearing potential (i.e., physiologically incapable of becoming pregnant) is defined as any female who has had a hysterectomy, bilateral oophorectomy (ovariectomy) or bilateral tubal ligation, or is post-menopausal.

A practical definition accepts menopause after 1 year without menses with an appropriate clinical profile, e.g., age appropriate, >45 years in the absence of hormone-replacement therapy (HRT). In questionable cases, the subject must have a follicle-stimulating hormone (FSH) value >40 mIU/mL and an estradiol value <40 pg/mL (<140 pmol/L).

A female of child-bearing potential is defined as any female who does not meet the criteria of non-childbearing potential as described in the previous paragraph.

If a female subject is of childbearing potential, she must have a serum β -human chorionic gonadotropin (HCG) pregnancy test performed within 14 days of first dose of study treatment. Subjects with a positive pregnancy test result must be excluded from the study. Subjects with a negative pregnancy test result must agree to use an effective contraception method as described below throughout the treatment period and for 16 weeks after stopping treatment with trametinib or 2 weeks after stopping treatment with dabrafenib monotherapy, whichever is longer.

Novartis-acceptable contraceptive methods, when used consistently and in accordance with both the product label and the instructions of the physician, are as follows:

- Placement of a hormonal or non-hormonal intrauterine device (IUD) or intrauterine system (IUS) with a documented failure rate of less than 1% per year.
- Sterilization (at least 6 months prior to screening) for male partners. The vasectomized male partner should be the sole partner for that subject.
- Total abstinence (when in line with the preferred and usual lifestyle of the subject). Periodic abstinence (e.g. calendar, ovulation, symptothermal, post-ovulation methods), and withdrawal are not acceptable methods of contraception.

- Female sterilization (have had surgical bilateral oophorectomy with or without hysterectomy), total hysterectomy, or tubal ligation at least six weeks before taking study treatment. In case of oophorectomy alone, only when the reproductive status of the woman has been confirmed by follow up hormone level assessment.

Notes:

- Double-barrier contraception: condom and occlusive cap (diaphragm or cervical/vault caps) with a vaginal spermicidal agent (foam/gel/cream/suppository) are not considered highly effective methods of contraception.
- Hormonal-based methods (e.g., oral contraceptives) are not considered as highly effective methods of contraception due to potential drug-drug interactions with dabrafenib and/or trametinib.
- Women are considered post-menopausal and not of child bearing potential if they have had 12 months of natural (spontaneous) amenorrhea with an appropriate clinical profile (i.e. age appropriate, history of vasomotor symptoms) or have had surgical bilateral oophorectomy (with or without hysterectomy), total hysterectomy, or tubal ligation at least six weeks ago. In the case of oophorectomy alone, only when the reproductive status of the woman has been confirmed by follow up hormone level assessment is she considered not of child bearing potential.

Female subjects who are lactating must discontinue nursing prior to enrollment and must refrain from nursing throughout the treatment period and for 30 days after the last dose of study treatment.

Male contraception

Dabrafenib may cause infertility in males, which may be irreversible.

Adverse effects of trametinib on male reproductive organs have been seen in animals. Male patients (including those that have had a vasectomy) taking the dabrafenib and trametinib combination therapy must use a condom during intercourse, and for 16 weeks after stopping treatment, and should not father a child during these periods.

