4.1.2 Inclusion Criteria

Specific information regarding warnings, precautions, contraindications, adverse events, and other pertinent information on the Novartis investigational product or other study treatment that may impact subject eligibility is provided in the trametinib and dabrafenib and trametinib combination IB's.

Deviations from inclusion criteria are not allowed because they can potentially jeopardize the scientific integrity of the study, regulatory acceptability or subject safety. Therefore, adherence to the criteria as specified in the protocol is essential.

Subjects eligible for enrolment in the study must meet all of the following criteria:

1. Signed written informed consent, which includes compliance with the requirements and restrictions listed in the consent form.
2. ≥ 18 years of age,
3. Histologically confirmed acral lentiginous or cutaneous melanoma that is either Stage IIIC (unresectable) or Stage IV (metastatic), and determined to be BRAF V600 mutation-positive by a central reference laboratory. Subjects with ocular or mucosal melanoma are not eligible.
4. Measurable disease (i.e., present with at least one measurable lesion) by RECIST version 1.1 [Eisenhauer EA 2009] by investigator's assessment. Refer to Section 7.2.3 for the definition of a measurable lesion.
5. Performance status score of 0 or 1 according to the Eastern Cooperative Oncology Group (ECOG) scale [Oken MM 1982].
6. All prior anti-cancer treatment-related toxicities (except alopecia and laboratory values as listed on Table 2) must be \leq Grade 1 according to the Common Terminology Criteria for Adverse Events version 4 (CTCAE version 4.0) at the time of enrolment [NCI 2009].
7. Able to swallow and retain oral medication and must not have any clinically significant gastrointestinal abnormalities that may alter absorption such as malabsorption syndrome or major resection of the stomach or bowels.
8. Women of child-bearing potential (see Section 7.3.7 for definitions) must have a negative serum pregnancy test within 14 days of first dose of study treatment and agree to use effective contraception, as stated in Section 7.3.7 from 14 days prior to enrolment, throughout the treatment period and for 4 months after the last dose of study treatment.
9. Adequate baseline organ function as defined in Table 2.
10. Subjects with East Asian origin.

Table 2 Definitions for Adequate Baseline Organ Function

System	Laboratory Values
Hematologic^a	
ANC	$\geq 1.2 \times 10^9/L$

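### Section 7.3.7.1 carries two conflicting surgical definitions of non-childbearing potential, so whether some women must use contraception depends on the paragraph read

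*Protocol*

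**What the plan says.** Inclusion criterion 8 (Protocol Section 4.1.2) takes its definition from another section: "Women of child-bearing potential (see Section 7.3.7 for definitions) must have a negative serum pregnancy test". It also requires effective contraception from these women. The opening of Section 4.1.2 allows no deviations from the inclusion criteria.

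Section 7.3.7.1 then defines the group twice.

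- **Body text.** A female of non-childbearing potential is "defined as any female who has had a hysterectomy, bilateral oophorectomy (ovariectomy) or bilateral tubal ligation, or is post-menopausal". No interval since surgery and no hormone result is asked for. Childbearing potential is defined as failing these criteria.
- **Notes.** Oophorectomy, total hysterectomy or tubal ligation counts if done at least six weeks ago, with a further condition: "In the case of oophorectomy alone, only when the reproductive status of the woman has been confirmed by follow up hormone level assessment" does the woman count as non-childbearing.

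On methods, the accepted list includes "Placement of a hormonal or non-hormonal intrauterine device (IUD) or intrauterine system (IUS"), subject to a failure rate below 1% per year. The Notes say: "Hormonal-based methods (e.g., oral contraceptives) are not considered as highly effective methods of contraception", and give possible drug interactions as the reason.

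On testing, Section 7.3.7.1 opens with "The need for a screening pregnancy test depends on whether a female subject is of childbearing potential or non-childbearing potential". Three other places state the screening serum test without that qualifier: the introductory text of Section 7, which makes central serum pregnancy results a condition of eligibility; Table 20, footnote 20; and Section 7.3.11.

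**The concern.** A definition that fixes who must use contraception should give one answer for each woman. Here two paragraphs of one section, both in force, can give opposite answers, and the criterion that depends on them does not say which governs. Two sites could classify the same woman differently and each cite the protocol. The section exists to prevent fetal exposure to study treatment, so the consequence is a safety obligation that applies or lapses according to where the investigator stopped reading. The uneven testing statements and the unqualified note on hormonal methods add to the uncertainty, but they are secondary.

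**Working it through.** No sample size, power or event count is involved, so the check sets the texts side by side.

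**Step 1. Classify the same woman under each paragraph.**

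| Case | Body text | Notes |
|---|---|---|
| Tubal ligation three weeks ago | Non-childbearing; no contraception duty | Six-week condition not met; duty applies |
| Bilateral oophorectomy alone, no hormone result | Non-childbearing; no contraception duty | Hormone condition not met; duty applies |
| Hysterectomy | Any hysterectomy qualifies | Must be total, and is subject to the six-week wording |
| Tubal ligation a year ago | Non-childbearing | Non-childbearing |

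The first two rows flip. The words *only when* in the hormone sentence set a condition, so the Note is not a restatement of the body text. In the Notes the six-week phrase follows the last item of a list. It covers tubal ligation on any reading and is most naturally read as covering all three operations.

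**Step 2. Does the text say which paragraph governs?** The body text defines childbearing potential by reference to the previous paragraph, which favours it as the formal anchor. But the paragraph immediately before that sentence is the one on menopause; the surgical criteria stand one paragraph further back. Criterion 8 points to Section 7.3.7 as a whole. The accepted-methods list also includes female sterilization with the same six-week and hormone conditions as the Notes. A woman who meets those conditions is non-childbearing under both definitions and needs no method, so the entry does not settle the matter. It does show that the conditioned wording is not a stray line.

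**Step 3. Menopause.** The body text asks for one year without menses and a suitable clinical profile, with "age appropriate, >45 years in the absence of hormone-replacement therapy (HRT") as an example, and adds: "In questionable cases, the subject must have a follicle-stimulating hormone (FSH) value >40 mIU/mL and an estradiol value <40 pg/mL". The Notes ask for 12 months of spontaneous amenorrhea and a suitable profile, with vasomotor symptoms as an example, and are silent on questionable cases. The two differ in examples and in that silence; they do not contradict each other.

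**Step 4. Hormonal methods.** Compare the accepted list with the Note. The only overlap is the hormonal intrauterine device or system. Oral contraceptives are on no accepted list. The requirement in the body text is an *effective* method from the list, while the Note speaks of *highly effective* methods, so the Note's bearing on the device is unclear.

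**Step 5. Testing.** Criterion 8 and Section 7.3.7.1 limit the serum test to women of childbearing potential. The Section 7 introduction, Table 20 footnote 20 and Section 7.3.11 do not. Exclusion criterion 16 separately bars pregnant women.

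**Step 6. Reach.** Exclusion criterion 2 bars major surgery within 21 days before enrollment. Six weeks is 42 days. If the operation counts as major, the conflict over timing covers about 42 − 21 = 21 days; if it does not, it covers the full 42. The protocol does not define major surgery. The hormone-result conflict has no such limit. The number of women is not given. Assuming half of 65, that is 0.5 × 65 = 32.5, or about 32. If 0% to 6% of them fall in a disputed category, the count is 0 to about 2 (0.06 × 32.5 = 1.95). Both the half and the 6% are assumptions.

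**The case against.** The strongest reply has three parts.

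First, a reader might infer that a woman could be enrolled and dosed with no pregnancy test. The documents do not support that as a clean consequence. The Section 7 introduction makes a serum result a condition of eligibility, and Table 20 footnote 20 and Section 7.3.11 require the screening test with no childbearing qualifier. This part stands, although it leaves those places at odds with criterion 8 and Section 7.3.7.1. It does not touch the contraception duty.

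Second, a reader might infer that the section both accepts and rejects hormonal contraception. It does not: one device is accepted, oral contraceptives never are. The Note's example and the Amendment 7 rationale in Appendix 8 both speak of oral contraceptives, so a narrower intent is plausible. What remains is an ambiguity about one method. The menopause wording likewise falls short of a contradiction.

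Third, timing. SAP Section 1.1 puts the primary analysis cut-off at 23-Feb-2018, after all subjects had been followed for 16 weeks, had two tumor assessments or had discontinued. Enrollment was therefore complete before Amendments 7 (15-Feb-2019) and 8 (27-Nov-2019). SAP Section 2.1.1 gives the last visit as 19-Apr-2021. The present text cannot have decided anyone's entry, and no effect on past enrollment can be asserted from it. This limits the practical weight. It does not remove a contradiction from the governing text, which also sets contraception duties during and after treatment.

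**Conclusion.** The two surgical definitions conflict, and the conflict changes whether certain women must use contraception. That conclusion rests on the wording alone. The screening-test statements are inconsistent between sections, and the status of the hormonal intrauterine device under the Note is unclear; both are lesser points. The stronger claims, that a woman could go untested or that hormonal contraception is accepted and rejected in general, are not supported.

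The reach is small: perhaps 0 to 2 subjects on the assumptions shown, with no figure in the documents to confirm it. No endpoint, estimate or analysis set is affected. This is a minor, safety-relevant wording inconsistency. The documents do not establish which definition was intended, and this review takes no position on that.

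**What to change.** Reconcile the body text and the Notes of Section 7.3.7.1 into a single definition of non-childbearing potential and delete the other. Have inclusion criterion 8, the opening of Section 7.3.7.1, the Section 7 introduction, Table 20 footnote 20 and Section 7.3.11 all refer to it, and say in the same terms who has the screening serum test. State explicitly whether the Note on hormonal-based methods applies to the listed hormonal intrauterine device or system. The sponsor's clinical and safety team decides which version stands on each of these.

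The cost is protocol wording only, in an amendment or a clarification letter, with no change to data collection or analysis. Since the SAP shows the last visit as past, the benefit is mainly a consistent record and clean text for any later protocol that reuses this section.
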